4.2.4. Exclusion Criteria

Candidates will be excluded from the study for **any** of the following reasons:

- (1) Concurrent clinically significant cardiovascular, hematological, renal, neurologic, hepatic, endocrine, psychiatric, or malignant diseases.
- (2) Known intolerance or hypersensitivity to any component of the study drugs (i.e., Epinephrine, Albuterol Sulfate or any sympathomimetic drugs, HFA-134a, thymol, ethanol, ascorbic acid, nitric acid, and hydrochloric acid).
- (3) Upper or lower respiratory tract infection, or other systemic infection within 6 weeks prior to Screening;
- (4) Clinically significant abnormalities in the screening/baseline ECG; prolonged corrected QT interval (QTcF) on ECG: men >450ms, women: >470ms; single or multiple premature ventricular contractions (PVC);
- (5) Abnormal thyroid function test (if TSH is out of range, refer to T3/T4 for thyroid function assessment);
- (6) Subject has been on other investigational drug/device studies within 30 days of Screening Visit or planned participation in another investigational drug trial at any time during this trial;
- (7) Women who are pregnant or lactating or planning a pregnancy during the study period;
- (8) Subject has donated or lost > 500 mL of blood within 3 months of Screening;
- (9) Evidence of alcohol or drug abuse or dependency within 6 months prior to screening; or
- (10) Use of any of the prohibited drugs listed in [Appendix III](#) without appropriate washout.

4.3. *Randomization Procedures*

4.3.1. Subject Identification Assignment

Subject will sign informed consent and be assigned a screening ID, as

EIS-mm,

where ***EI*** represents “E004-CL-I”, ***S*** stands for screening, and ***mm*** is the screening sequential number. The subject will be evaluated per inclusion/exclusion criteria. The

following procedures will be performed at Screening: (i) physical examination (PE), (ii) measurements of vital signs, (iii) ECG, (iv) urinalysis (UA), (v) urine drug screen, (vi) alcohol screen (urine or breathalyzer), (vii) urine or serum pregnancy test (female subjects), and (viii) fasting (≥ 8 hours) blood tests [comprehensive metabolic panel, complete blood count (CBC) with differentials, thyroid function tests, HIV, hepatitis B and C tests].

After satisfying the enrollment criteria, subjects will be assigned a unique subject ID as

EIPK-nn,

where ***nn*** is the sequential number in order of enrollment.

The same Subject ID will be used throughout the Dosing Visits. The Subject ID numbers will be recorded on the study source documents, the case report forms, and other appropriate study documents. In addition, all subjects will be identified by their first, (middle), and last initials.

4.3.2. Subject Randomization

The Investigator must ensure that all inclusion/exclusion criteria are met, and will endorse the subject enrollment at the beginning of Dosing Visit 1.

A set of computer generated randomization codes will be supplied by Amphastar IT department in accordance with the Standard Operating Procedure (SOP). A 3×3 Latin Square method will be used for randomization. The randomization code will dictate the sequence of the three (3) crossover treatments for individual subject.

4.4. Dispensing, Returning, and Storage of Material and Drug Supplies

All study drug units are prepared and packaged as individual units by the Amphastar manufacturing team under GMP conditions and QA oversight. Study drugs will be packaged and delivered to the investigational site. All study units are labeled with proper subject ID#, and Visit#, but are devoid of any treatment-identifying information.

Study drugs will be properly labeled and delivered to the dosing area for immediate use. All study drug units must be returned to the site or designee when the visit is completed, and its use documented.

At each Dosing Visit, one (1) study treatment (Treatment-A, B, or C) will be assigned to subjects per the randomization code (**Table 1**).

Table 1. Treatments and Dose

Items	Treatment-A	Treatment-B	Treatment-C
Study Drug Name	Primatene Mist, E004	Epinephrine Injection Auto-Injector (Generic of EpiPen®)	ProAir
Manufacturer			
API	Epinephrine	Epinephrine	Albuterol Sulfate
Dosage Form	Microcrystalline Suspension HFA MDI	Sterile Solution	Microcrystalline Suspension HFA MDI
Strength	0.125 mg/inh	0.3mg/0.3mL	0.09 mg/inh
Dose Regimen	2 inhalations, 0.25mg	IM Injection of 0.30 mg Epinephrine in 0.30 mL	2 inhalations, 0.180 mg
Route of Administration	Oral Inhalation	IM Injection	Oral Inhalation

Study drugs should be stored at USP defined, controlled room temperature, with excursions permitted from 15°-25°C (59°-77°F). The study drugs will be protected from environmental extremes and stored in a locked cabinet or room to which only designated persons have access. The inhalers will be stored with the mouthpiece down.

4.5. Study Drugs Administration and Training

4.5.1. Training for Correct Use of MDI Inhaler

During the Screening and at the beginning of every Dosing Visit, each subject will be trained on the correct use of the MDI inhalation aerosols in a standard fashion to assure a relatively consistent inspiratory flow rate and duration. A video on how to use the MDI will be provided at each training session. The training will use placebo, a MDI simulation unit that contains no active drug. Subjects have to demonstrate a consistent inhalation time >2.0 seconds (at least 3 times, with a maximum of 5 attempts) after training. Vitalograph AIM™ (Aerosol Inhalation Monitor) will be used to monitor and measure the duration of the inhalation during the training at Screening and prior to dosing.

4.5.2. Preparation and Training of MDIs at the Dosing Visit

Each MDI must be primed at the study site prior to the first use by releasing 4 test sprays (E004 for Treatment-A), or 3 test sprays (ProAir for Treatment-C) into the air away from the face, **shaking well before each spray**. Priming will be performed in an area that is well ventilated (preferably a fume hood, or an open space), and physically separated from the study evaluation area. Refer to the training video for details on the priming procedure.

- (1) **Correct sitting position:** In order to get a deep proper breath during dosing, the subject must sit on a stool, not a chair, with their posture straight in a relaxed calm state for at least 1 min prior to dosing. Do not slouch or lean forward or backward.
- (2) **Finger placement for dosing:** To ensure proper drug delivery, subject is required to hold the canister with the thumb at the bottom and place the index finger of the same hand on the top of the canister to release the drug. For each actuation, subject **must fully depress the top of the metal canister, and hold it for at least one second before releasing.**
- (3) **Critical Timing:** Subject begins a **slow and deep inhalation before pressing the inhaler.** A slight delay in the sequence can result in deposition of inhaled drugs on the back of the throat and tongue.
- (4) **Deep inhalation as long as possible:** After pressing the inhaler, subject should continue to inhale slowly and deeply for as long as possible (at least 3-5 seconds, refer to the training video). Keep tongue away from the opening of the mouthpiece.
- (5) After deep inhalation, **hold the breath for approximately 10 seconds** (5- 10 seconds)
^[6] to allow deposition of drug particles into the lower level of the lung.

4.5.3. Detailed MDI Dosing Procedure

- (1) The designated study site personnel will verify if the canister is fully inserted into the actuator.
- (2) The designated study site personnel will remove the cap from the mouthpiece of the actuator, and check the mouthpiece for foreign objects prior to use;
- (3) Subjects will **first shake and spray into the air one time to mix the medicine.**
- (4) Subjects will exhale deeply through the mouth and empty the lungs as completely as possible by exhaling fully (exhalation must be deep and slow, similar to the deep inhalation step);
- (5) Immediately after the full exhalation, subjects will hold the inhaler with the mouthpiece down, then places the mouthpiece fully into their mouth, with lips sealed around the mouthpiece;
- (6) While inhaling, subjects will fully depress the top of the canister with an index finger. Subjects should keep inhaling **deeply and slowly for as long as possible (at least 3-5 seconds)** through the mouth;
- (7) After breathing in fully, remove the inhaler from the mouth, subjects keep the mouth closed, hold the breath for approximately 10 seconds (5- 10 seconds)
^[6];
- (8) Subjects will exhale slowly through the nose (keep lips nearly closed); and
- (9) Repeat the above (1) to (7) steps for the second inhalation. The time interval between each actuation will be within 30 seconds.

4.5.4. IM Injection Procedure

IM injection (0.30mg of epinephrine solution in 0.30 mL) for Treatment-B will be given on the thigh. Subjects will be lying down in a supine position. The 0.30 mL dose will be given perpendicularly as a single deep IM injection into anterolateral aspect of the thigh (vastus lateralis site). Epinephrine auto-injector (Treatment B) will be administered as follows [2]:

- (1) Doser or designated site personnel will quickly twist off the yellow cap off the auto-injector.
- (2) Subject will hold the leg firmly in place.
- (3) Doser or designated site personnel will first pull off the blue safety release to unlock the auto injector.
- (4) Doser will place the orange tip against the middle of the outer thigh (upper leg) at a right angle (perpendicular) to the thigh.
- (5) Swing and push the injector firmly until it ‘clicks.’ The click signals that the injection has started.
- (6) Hold firmly in place for 3 seconds. Time 0 begins once the holding is completed.
- (7) Remove the injector from the thigh and massage (apply gentle pressure) with dry gauze to the injection area for 10 seconds. The orange tip automatically extends out after use.
- (8) The injection site will be observed for any medication leakage for approximately 30 seconds after the dosing is completed. If there is observed leakage, PK samples will not be collected, subject will be early terminated (ET).

4.6. Blinding Methodology and Procedure

The preparation area will be physically separated from the dosing area to ensure the evaluator remains blinded. All treatments will be prepared by qualified personnel at the study site prior to dosing at each study visit according to the order of treatment arms assigned to subjects per the randomization code. Subjects will be escorted to a separated dosing area for study drug administration to preserve blinding from evaluators.

Study drugs will be dispensed by CRC or pharmacist per randomization.

Safety evaluator(s) will remain blinded during the course of the study and will have the sole responsibility of evaluating any Adverse events.

4.7. Unblinding

Should any safety evaluator become “unblinded” to any subject’s treatment assignment during the study, the Investigator shall notify Amphastar Clinical Research Department within 24 hours. The Justification for Code Breaking Form will be signed and dated by the

Investigator, and the Amphastar Clinical Research Associate (CRA). The form will be placed back into the envelope, which is not to be resealed, and kept in study site regulatory files, separated from the other envelopes. Any subject whose envelope seal has been broken will be subject to QA audit and may be excluded from the BE data analyses. Subject should also be reminded to maintain the identity/configuration of the study drug provided to them and must not disclose this information to the blinded study team or other subjects in order to maintain the blinding of the evaluators.

5. STUDY PROCEDURE

5.1. *Global Plan*

The design includes (i) a Screening Visit (3-7 days prior to Visit-1), (ii) three (3) Dosing Visits separated by a 2-7 day washout period, and (iii) a post-study follow-up evaluation 1-7 days after Dosing Visit-3 or study termination.

5.2. *Screening Procedure and Scheduling*

5.2.1. Schedule and Purpose of Screening Visit

The Screening Visit takes place 3-7 days prior to Dosing Visit-1. During Screening, subject qualification will be determined based on the Inclusion/Exclusion Criteria ([Sections 4.2.3](#) and [4.2.4](#)), the physical examination, and laboratory test results. These data will be documented on the subject source documents.

5.2.2. Informed Consent Form

The Informed Consent document will be used to explain the purpose, risks, and benefits of study participation to the subject in simple terms at the Screening Visit. The Investigator must obtain a signed informed consent form from each subject before proceeding to any screening and study activities. A copy of the signed Informed Consent Form should be given to the subject. The Informed Consent Form includes compliance with the privacy provisions of HIPAA.

5.2.3. Medical History, PE, and General Safety (Screening Activities)

The Screening Visit entails the following screening activities:

- (1) Interview for demographic information and medical history;
- (2) Body Mass Index (BMI) needs to meet the requirements in [Section 4.2.3](#). BMI can be calculated and checked by the formula and chart in [Appendix II](#), or by utilizing the NIH website;
- (3) Review medication history for any prohibited drugs ([Appendix III](#)). Ensure any appropriate washout has been observed;
- (4) A full physical examination and measurements of vital signs will be performed to ensure that the subject is generally healthy;
- (5) The subject has to rest in a secluded area for at least 10 minutes before measurements of vital signs. The blood pressure and heart rate measurement can be repeated twice, each separated by a 15 minute interval;

- (6) 12-lead ECG will be conducted (routine and QT/QTc) to ensure absence of overt cardiac illnesses;
- (7) Collect urine samples for urinalysis (routine and microscopic), alcohol/drug screens (urine or breathalyzer test allowed for alcohol) for all subjects, and pregnancy test for all female subjects (serum pregnancy test allowed);
- (8) Collect blood samples for CBC, thyroid function, HIV-Ab, HBs-Ag, and HCV-Ab tests;
- (9) Collect fasting (≥ 8 hours) blood samples for serum comprehensive metabolic panel (per [Appendix IV](#)); and
- (10) At the Screening Visit, subjects should be trained on the use of the MDI inhalation aerosols in a standard fashion to assure a relatively consistent inspiratory flow rate and inspiratory duration as described in [Section 4.5](#). Eligible subjects must demonstrate the correct use of the MDI unit and a consistent inhalation time >2.0 seconds after training, for at least three (3) times, with a maximum of 5 attempts. AIM™ (Aerosol Inhalation Monitor) will be used to monitor and measure the duration of the inhalation during the training at Screening and prior to dosing.

Out of range lab results may be repeated once at the discretion of the Investigator. Subject enrollment will be confirmed at the beginning of Dosing Visit-1 ([Section 5.3.1](#)). The final decision of enrollment will be determined by the Investigator.

5.2.4. Instruction to Subjects at the End of Screening Visit

- (1) Dates for Dosing Visit-1, Visit-2, and Visit-3 should be separated by 2 to 7 days.
- (2) Subject must be at least 10-hours fasting for each Dosing Visit.
- (3) Subjects must refrain from alcohol consumption and caffeine-containing (including decaffeinated) beverages or foods (coffee, tea, applicable soft drinks including cola and analogs, or chocolate) for 24 hours prior to each Dosing Visit.
- (4) At each Dosing Visit, subjects are required to check in at the site the night before. Dinner will be provided at study site.

5.3. Dosing Visits

5.3.1. General Profile for Dosing Visits

The same procedures will be performed at each Dosing Visit, except that the subject will be given different study treatments based on the randomization code.

At Dosing Visit-1 the following activities will be conducted:

- (1) Enrollment is verified at the beginning of Dosing Visit-1, by reviewing all inclusion/exclusion criteria and other requirements.

(2) Upon verification of subject enrollment, a Subject ID will be assigned and the randomization procedure will be completed (see [Section 4.3.1](#) and [4.3.2](#))

5.3.2. Pre-dose Activities

At each Dosing Visit, the following review and verification will be performed prior to study drug administration:

- (1) A urine or serum pregnancy test must be performed on all female subjects. If it is positive, the subject will be terminated from the study;
- (2) Any concomitant medication since the last visit will be recorded, including name of medication, route of administration, dosage, indication, and start and end dates where available. If any medications listed in [Appendix III](#) were used after the last visit without the proper washout period, the subject will be terminated;
- (3) Perform alcohol and drug test; if any is positive, subject will be terminated;
- (4) Subjects will be trained again on the use of the MDI inhalation aerosols prior to each treatment session, as described in [Section 4.5.1](#);
- (5) Placement of ECG leads;
- (6) Subjects need to rest for at least 10 minutes prior to the baseline vital signs evaluations. Vital signs should be taken from the opposite arm of the IV catheter arm if possible; Vital signs measurement may be repeated twice to PI discretion.
- (7) An indwelling IV catheter shall be placed into one of the antecubital region veins for blood drawing, or separate venipunctures may be used; and
- (8) One (1) baseline blood samples will be collected within 30 minutes before dosing.

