- (12) Demonstrate proficiency in the use of MDI and a consistent inhalation time >2.0 seconds after training, for at least three (3) times, with a maximum of 5 attempts.

Exclusion Criteria:

- 1) Concurrent clinically significant cardiovascular, hematological, renal, neurologic, hepatic, endocrine, psychiatric, or malignant diseases.
- 2) Known intolerance or hypersensitivity to any component of the study drugs (i.e., Epinephrine, Albuterol Sulfate or any sympathomimetic drugs, HFA-134a, thymol, ethanol, ascorbic acid, nitric acid, and hydrochloric acid).
- 3) Upper or lower respiratory tract infection, or other systemic infection within 6 weeks prior to Screening;
- 4) Clinically significant abnormalities in the screening/baseline ECG; prolonged corrected QT interval (QTcF) on ECG: men >450ms, women: >470ms; single or multiple premature ventricular contractions (PVC);
- 5) Abnormal thyroid function test (if TSH is out of range, refer to T3/T4 for thyroid function assessment);
- 6) Subject has been on other investigational drug/device studies within 30 days of Screening Visit or planned participation in another investigational drug trial at any time during this trial;
- 7) Women who are pregnant or lactating or planning a pregnancy during the study period;
- 8) Subject has donated or lost > 500 mL of blood within 3 months of Screening;
- 9) Evidence of alcohol or drug abuse or dependency within 6 months prior to screening; or
- 10) Use of any of the prohibited drugs listed in [Appendix III](#) without appropriate washout.

III. Study Drugs and Dosing Regimens

Qualified subjects will participate in three (3) dosing visits separated by a period of 2 – 7 days. Each subject will receive one study treatment at each dosing visit per the randomized sequences, as described in **Table A**.

MDIs will be dispensed by the designated site professional, and the correctness of the initial dose indicator mark shall be verified prior to dispensing. The reading on the dose indicator of each MDI unit will be recorded prior to and after dosing in the study source documents. IM injection will be dispensed using aseptic techniques by the designated site personnel.

Due to the difference in dosing position for IM and oral inhalation, and to preserve blinding from evaluators, subjects will be escorted to a separated dosing area for study drug administration.

Table A. Study Arms and Treatments

Items	Treatment-A	Treatment-B	Treatment-C

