1.4. Pharmacokinetics (PK) and Pharmacodynamics (PD) Profile

Pharmacokinetics:

The absorption of inhaled epinephrine is rapid. In a multiple-dose systemic absorption of inhaled epinephrine study which enrolled six normal healthy volunteers, a rapid rise of plasma epinephrine levels with short duration were observed after administration of 15 puffs

followed by 30 puffs, with a >5 minute interval, at 160 mcg per puff. One minute after the initial 15 inhalations (2.4 mg) of epinephrine, the mean base-line epinephrine levels rose from 0.23 (± 0.02) to a peak of 1.50(± 0.61) nmol/L (i.e., 275 pg/ml). One minute after the subsequent 30 inhalations (a dose of 4.8 mg epinephrine), the epinephrine level rose to a peak of 4.22 (1.93) nmol/L (i.e., 772 pg/ml). The plasma epinephrine fell to baseline at 20 min after 30 inhalations of epinephrine ^[2].

Overall systemic sympathomimetic effects are minimized due to a very low systemic exposure (~5% bioavailability) after oral inhalation ^[3].

The systemic levels of albuterol are low after inhalation of recommended doses. The terminal plasma half-life of albuterol delivered by PROAIR HFA was approximately 6 hours.

Information from published literature suggests that the primary enzyme responsible for the metabolism of albuterol in humans is SULT1A3 (sulfotransferase). The primary route of elimination of albuterol is through renal excretion (80% to 100%) of either the parent compound or the primary metabolite. Less than 20% of the drug is detected in the feces.

Pharmacodynamics:

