4. CALCULATION OF RELATED STATISTICAL QUANTITIES

4.1 PK/PD PARAMETERS

4.1.1 Primary Endpoints

(1) C_{max} , in units of pg/mL, is defined as the maximum of experimental data points of epinephrine or albuterol concentration for a given subject and given treatment:

[figure not shown]
$$C_{max} = \max (C_1 \cdots C_i \cdots C_n) \quad i = 1, 2, 3 \cdots n \quad (1)$$

where C_i is the observed plasma concentration of albuterol or epinephrine at the time t_i ; which is the sampling point time;
 t_1 is the baseline, and n is the number of available PK measurements.

(2) $AUC_{0-t_m}^{Tot}$ for Total API,

As is demonstrated in the left plot of **Figure 1**, the AUC is for total API, including both exogenous and endogenous, if the endogenous active ingredient exists, such as epinephrine for Treatments A and B.

Figure 1 AUC for Total Active Ingredient (left) and Drug Exposure (right)

$AUC_{0-t_m}^{Tot}$ is reported in units of pg/mL*hr, can be calculated per the trapezoidal rule as given the Eq. (2):

$$AUC_{0-t_m}^{Tot} = \sum_{i=1}^{m-1} \frac{C_i + C_{i+1}}{2} (t_{i+1} - t_i) \quad (2)$$

where

- t_m is the time of the first PK point for the subject and the treatment, after C_{max} , that is reduced to the same day baseline (C_0), if C_0 is detectable, such as for epinephrine, (see **Fig. 1**, left plot); and
- $t_m > t_{max}$, and is the smallest time point that meets

$$C(t_m) \leq C_0 + \frac{1}{2} QL \quad (3)$$

- $t_m = 24$ hrs for albuterol, or m is the number of available PK measurements until t_m .

(3) The AUC for Drug Exposure $AUC_{0-t_m}^{DE}$

The AUC for the drug exposure, as is demonstrated in the right plot of **Figure 1**, is the AUC for exogenous API, if the endogenous active ingredient exist such as epinephrine for Treatments A and B.

$AUC_{0-t_m}^{DE}$ is reported in units of pg/mL*hr, and is calculated as follows:

$$AUC_{0-t_m}^{DE} = AUC_{0-t_m}^{Tot} - C_0 t_m \quad (4)$$

where $AUC_{0-t_m}^{Tot}$ and t_m is obtained based on Eqs. (2) and (3).

(4) **Drug Exposure $AUC_{0-\infty}$** (in units of pg/mL*min) is defined as below

$$\begin{cases} AUC_{0-\infty} = AUC_{0-t_m}^{DE} & \text{if } t_m < 24 \text{ hrs} \\ AUC_{0-\infty} = AUC_{0-t_m}^{DE} + AUC_{t_m-\infty}^{DE} & \text{if } t_m = 24 \text{ hrs} \end{cases} \quad (5)$$

$AUC_{t_m-\infty}$ can be obtained per the extrapolation method as given in the Eqs. (6) –(7) below, based on the time is long enough so that

$$C(t) \approx Be^{-k_e t}, \quad (6)$$

thus

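### One pre-dose sample, drawn without a set rest, place or posture, is the SAP's only correction for endogenous epinephrine in the AUC, and Primatene exposure is sensitive to its error

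*Protocol*

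**What the plan says.** **Sampling (Protocol 5.3.2).** Item (8): "One (1) baseline blood samples will be collected within 30 minutes before dosing". Table 2 in Protocol 5.3.5 agrees: one baseline and 25 post-dose samples. Item (7), listed just before, reads: "An indwelling IV catheter shall be placed into one of the antecubital region veins for blood drawing, or separate venipunctures may be used". No interval between the two is stated. The only rest is in item (6) and belongs to another measurement: "Subjects need to rest for at least 10 minutes prior to the baseline vital signs evaluations".

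**Place and posture.** Protocol 4.6: "Subjects will be escorted to a separated dosing area for study drug administration to preserve blinding from evaluators". Where the baseline sample is drawn is not stated. Dosing is on a stool for the inhalers (4.5.2) and supine for IM (4.5.4). After dosing, 5.3.3 item (5) sets a semi-recumbent or seated position for 120 minutes for every treatment.

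**Use of the baseline (SAP 4.1.1).**
- Eq. 3: the end of integration, t_m, "is the time of the first PK point for the subject and the treatment, after" Cmax, at which the concentration is no higher than C0 + QL/2.
- Eq. 4: "AUC_{0-t_m}^{DE} = AUC_{0-t_m}^{Tot} - C_0 t_m".
- Eq. 5: for t_m below 24 h, AUC0-∞ is the same quantity, so it passes directly into relative bioavailability (SAP 5.3.2.3).
- Eq. 9: the fallback fit for Ke subtracts the same baseline.
- Cmax is the uncorrected maximum and does not use C0.

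SAP 5.1.1 requires the baseline point to be available for a subject to be evaluable. Neither document sets conditions for its quality.

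**The concern.** Epinephrine responds to needles, movement and posture. If C0 is not measured in the state that holds after dosing, the plan subtracts the wrong amount. Because C0 also decides when integration stops, one error acts twice. A high C0 removes too much and ends the AUC early. A low C0 removes too little and can keep the AUC running for hours.

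This matters most for Treatment A, where the drug signal may be no larger than the endogenous level. At stake are two SAP primary endpoints for epinephrine (AUC0-t and AUC0-∞) and the A/B relative bioavailability. Baseline conditions are not tied to the dosing posture, which differs between A and B, so the error need not cancel in the ratio.

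**Working it through.** **1. The plan's own figures (Protocol 1.4).** The unit conversion implied by the text is 275/1.50 = 183.3 and 772/4.22 = 182.9, so about 183.2 pg/mL per nmol/L. It reproduces the stated peaks: 1.50 × 183.2 = 275 and 4.22 × 183.2 = 773 pg/mL. The baseline is 0.23 × 183.2 = 42.1 pg/mL.

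**2. Expected rise at 0.25 mg (linear scaling).**
- From 2.4 mg: (1.50 − 0.23) × 183.2 × 0.25/2.4 = 24 pg/mL.
- From 4.8 mg: (4.22 − 0.23) × 183.2 × 0.25/4.8 = 38 pg/mL.

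**3. Simple error arithmetic.** Protocol 1.4 gives the duration: "The plasma epinephrine fell to baseline at 20 min after 30 inhalations of epinephrine". A 20-minute triangle has area peak × 20/2, which is 242 to 381 pg·min/mL (unrounded peaks 24.2 and 38.1). An error e in C0 shifts the AUC by e × 42.1 × 20.

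| Error in C0 | Shift (pg·min/mL) | Share of A exposure |
|---|---|---|
| 0.02 nmol/L read as SD (3.7 pg/mL) | 73 | 19–30% |
| 0.02 nmol/L read as SEM, n = 6 (SD 9.0 pg/mL) | 179 | 47–74% |
| 20%, assumed | 168 | 44–69% |
| 30%, assumed | 253 | 66–104% |

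The ± 0.02 is spread between subjects and is not labelled SD or SEM. It is only a rough guide to within-subject error.

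**4. The planned estimator.** Eqs. 2–4 were simulated on the 26-point schedule. Assumptions: baseline 42 pg/mL, peak 24 or 38 pg/mL at 1 to 2 min, half-life 4 to 4.5 min, independent lognormal sample-to-sample variation with CV 10–20%, QL 5–20 pg/mL.
- Individual A exposures wrong by more than half: about 12–60% with one baseline.
- At CV 20%: 37–60% with one baseline, 22–46% with the mean of three.
- Mean A exposure with random error only: about 0.8 to 6.4 times the truth, above it in most cases. Negative values: 0–5%.
- C0 systematically 20% high: median recovered exposure about 24–52% of truth, or about 75% if the peak is 100 pg/mL. For an illustrative IM profile (the documents give none; assumed peak 200 to 400 pg/mL at 15 min, half-life 30 min) about 90% is recovered.

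**5. Why the error is asymmetric.** Take peak 24, CV 10%, QL 5 and a true exposure of 150 pg·min/mL. With C0 10 pg/mL too high, the median AUC is 38. With C0 10 pg/mL too low, the stopping rule is usually never met, the median t_m is 24 h, and the AUC is about 13,600. That is close to the uncorrected residue of 10 × 1440 = 14,400.

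**The case against.** **Timing.** Protocol 5.3.2 is a checklist, not a timed sequence. Item (6) takes vital signs from the arm opposite the catheter where possible, which suggests that the catheter may already be in. A reader might infer that the baseline is drawn straight after the needle and before the move to the dosing area. The text allows this but does not require it; up to about 30 minutes may pass. What remains is that nothing prevents it.

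**Existing controls.** Activity is limited, post-dose posture is common to all treatments, and inhaler subjects sit calmly for at least 1 minute before dosing. These govern dosing and what follows, not the baseline draw.

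**The signal may be understated.** The cited peaks followed 15 and 30 serial puffs from a different inhaler, with elimination going on during dosing. Assuming 30 s per puff and a 4.5-minute half-life, the peaks per mg are damped 1.7- and 2.6-fold, so the scaled rise would be about 40 to 97 pg/mL. The second series also followed the first after an interval of only more than 5 minutes, so subtracting 0.23 nmol/L there is not clean. This stands, and is why the 100 pg/mL case is shown.

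**Direction.** The SAP Background expects much lower exposure after inhalation, and a reader might infer that the baseline error favours that result. This follows only if C0 is systematically high, which the documents do not show. Random error pushes mean A exposure upward in most of the simulated cases.

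**The stopping rule.** Much of the instability comes from t_m. Averaging reduces it without curing it: with three baselines at CV 20%, mean A exposure was still 0.9 to 2.9 times the truth.

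**Conclusion.** The point holds as a weakness of design. The documents establish that one pre-dose value per visit, taken under unspecified conditions, drives the subtraction, the stopping time and the Ke fallback. On the protocol's own literature figures the expected Primatene rise is of the same order as the baseline.

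The size is conditional. It rests on an assumed CV of 10–20%, an assumed QL of 5–20 pg/mL and linear dose scaling. Under those, about 12–60% of individual A exposures are wrong by more than half, and a C0 20% too high leaves about 24–52% of A exposure at the median. A larger true rise shrinks both effects.

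A reader might go further and say that the error is as large as the exposure itself. In the simple arithmetic that needs an error of about 30% in C0, and the documents give no within-subject variance to support or exclude it. The net direction of bias in A/B relative bioavailability is not known.

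**What to change.** 1. **Protocol 5.3.2.** Place the catheter first. Require a fixed rest (for example at least 20 minutes) before the baseline PK draw. Take that draw through the catheter, in the seated or semi-recumbent posture held after dosing. This addresses systematic error and needs no extra blood.
2. **Protocol 5.3.5 and SAP 4.1.1.** Take at least two pre-dose samples through that catheter and define C0 as their mean in Eqs. 3, 4 and 9. This addresses random error.
3. **SAP.** Add a sensitivity analysis that uses each subject's 0–120 min epinephrine profile from the Treatment C visit as a drug-free reference for A over a fixed interval. Protocol 5.3.5 and SAP 3.1 already plan both analytes at each visit. It assumes that albuterol does not materially change endogenous epinephrine. It avoids the dependence of t_m on C0 and needs no extra blood.

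**Cost.** About 20 minutes per visit, and about 6 mL per extra draw (5 mL plus 1 mL discarded). PK blood over three visits is now 26 × 6 × 3 = 468 mL. It becomes 27 × 6 × 3 = 486 mL with two baselines, or 28 × 6 × 3 = 504 mL with three, before safety laboratory draws. For scale, the protocol excludes candidates who lost more than 500 mL in the 3 months before screening. Choose the number of baselines within the site's blood-volume limit; if none can be added, changes 1 and 3 stand alone.
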